6.2 Potential Benefits/Advantages of Treatment/Product

Prior therapies, such as chronic anticoagulation or surgical bypass procedures, are either ineffective, or significantly invasive. The potential risks of venous stenting are those associated with any intra-vascular procedure up to and including death, although at lower rates than those typically seen for arterial procedures. With demonstrated primary patency rates of 60-90% through 12 months, and demonstrated serious adverse event rates of <1%, the benefits of the proposed study outweigh the potential risks.

Currently marketed venous stents have sufficient clinical data regarding their use in veins of the lower extremities and pelvis for the treatment of venous outflow obstruction in adults and their risk profiles are not known or considered to be different from the Veniti Vici Venous Stent.

STE-HUM-007P US Clinical Protocol Revision C

VENITI

7 STUDY OBJECTIVE AND DESIGN

The VIRTUS trial is a prospective, multicenter, single arm, non-randomized study to define safety and efficacy of the Veniti Vici Venous Stent System in relation to predefined Objective Performance goals. The objective of this study is to assess the safety and efficacy of the Veniti Vici Venous Stent System in achieving patency of the target venous lesion in patients who present with clinically significant chronic non-malignant occlusion of the iliofemoral venous outflow tract.

7.1 **Primary Endpoint – Efficacy:**

The primary efficacy endpoint for this study will be the primary patency rate at 12 months post-intervention, defined as freedom from occlusion by thrombosis AND freedom from surgical or endovascular intervention on target vessel which are found to have re-stenosis or stent occlusion to maintain patency AND freedom from in-stent stenosis more than 50% by venogram. For patients refusing the venographic assessment at 12 months, DUS-determined patency will be used instead.

7.2 Primary Endpoint – Safety:

The primary safety endpoint for this study will be a composite endpoint of any Major Adverse Event within 30 days, as adjudicated by a Clinical Events Committee. Major Adverse Events are listed in Section 11.1.4.

7.3 Secondary Endpoint – Efficacy:

The formal secondary endpoint of this study is a binary response variable based on whether or not a subject achieves at least 50% improvement on the Venous Clinical Severity Scoring (VCSS) scale at 12 months post-intervention.

7.4 Ancillary Outcomes:

Procedural Endpoints

- Procedural technical success, defined as achievement of a final residual target vessel diameter stenosis of ≤50% as measured on the postprocedural venogram, without skipped lesion regions, with placement of the study device alone with or without post-stenting balloon dilation as needed
- 2. Lesion success defined as achievement of ≤50% residual diameter stenosis using any percutaneous method (including the use of non-study devices)
- 3. Procedural success defined as procedural technical success without the occurrence of major adverse event between the index procedure and discharge
- 4. Late technical success (through 12 months) defined as:
 - a. Absence of migration
 - b. Absence of stent embolization
 - c. Achievement of primary patency
 - d. Structural integrity, defined as the absence of:
 - i. Pinching, defined as focal compression of the stent with > 50% diameter reduction of the stent

STE-HUM-007P US Clinical Protocol Revision C

Confidential

Page 23 of 70

- ii. Kinking, defined as >50% diameter reduction of the stent with the stent doubling or bending on itself
- iii. Recoil, defined a poor radial resistance to diffuse collapse, which results in >50% diameter reduction of the stent (i.e., stent diameters obtained throughout the study period as compared to the final stent diameter after insertion measured by DUS or venogram).
- Absence of fractures, which will be assessed as per Jaff, et al.1 (See Appendix 3.) Data to be collected for each fracture identified includes:

Limb (right or left) Venous segment(s) where fractures are located Overlapping versus non-overlapping Type of fracture (Type I, II, III, IV)

5. Subgroup analysis to evaluate device performance across genders.

Clinical Endpoints

- 6. Improvement in Venous Clinical Severity Scoring (VCSS) at 6 and 12 months
- 7. Improvements in Quality of Life (CIVIQ-2) at 12 months (See Appendix 5.)
- 8. Minor outcomes: complications occurring within 30 days of the procedure that do not meet the definition of an MAE, do not require hospitalization and do not delay discharge.

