Prior conservative therapies, such as chronic extended anticoagulation and compression, have been shown to be ineffective. Surgical bypass procedures are invasive with significant complication rate and have been exclusively performed as an end-stage procedure in the most severely compromised patients. Today open surgery is offered only to surgically fit patients with severe symptoms after unsuccessful or failed stenting.¹⁵ There are no, randomized or multicenter studies on venous stenting, but multiple single center large (over 50 patients) registries cohort studies ^{9 16 17 18} have reported technical success rates superior to 90% and patency rates of 79-98% at 5 years. ¹⁸ It is difficult to determine the exact expected patency rates from these studies, as these studies included different etiologies, extent of the disease, concomitant reflux and clinical status, typically do not state the degree of obstruction prior to procedure, have variability in inflow to the stent system and often base the definition of patency on duplex-scan. (There is no reported comparison between duplex ultrasound scanning and venography in the assessment of stent patency. Venography is, therefore, still considered the gold standard.) However, given the very high rate of recurrence of thrombotic disease or clinical deterioration after non-stenting approaches, even a patency rate of 50-60% would offer significant improvement over current approved therapy.

The data available indicate that stenting for chronic obstructive iliofemoral lesions comes with a very low risk. So far, in the published literature, neither death nor pulmonary embolism nor life-threatening complications have occurred. In the largest single-center report on 953 stented limbs with ultrasound guided venous access ¹⁶, there were only four access-related adverse events: three femoral artery pseudoaneurysms treated with thrombin injection alone, and one arteriovenous fistula^{5.} In addition to the access complications, there was one case where the guidewire became trapped in the stent and the stent/guidewire was removed via a cutdown of the femoral vein. In this large series, there were 47 thrombotic events that occurred over a 5-year period (5%).

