9.6 Discharge or Three Days Post-Procedure (whichever comes first)

- Duplex ultrasound to determine post-procedural target vessel lumen diameter (For patients refusing the venographic assessment at 12 months [or prior Interval Evaluation, as applicable], DUS-determined patency will be used instead, with the DUS obtained at the Discharge or Three Days Post-Procedure visit serving as the baseline).
- Determination of discharge
- Anticoagulation Review, based on the Extended Anticoagulation Protocol (See Appendix 2.)
- Adverse event assessment
- Patients who do not meet intra-procedural inclusion criteria (and who do not receive the implanted study device) should be followed only through hospital discharge for protocol deviations and adverse events. This visit will conclude participation for these screen failed patients. These subjects will not be included in the statistical analysis.

9.7 1 Month Evaluation (30 days -7/+14 days)

- Physical examination (to assess for the presence of Adverse Events)
- Anticoagulation Review, based on the Extended Anticoagulation Protocol (See Appendix 2.)

9.8 6 Month Evaluation (180 days ± 30 days)

- Physical examination (to assess for the presence of Adverse Events)
- Duplex ultrasound (required only for first 30 patients to assess patency)
- CIVIQ-2 Quality of Life questionnaire (See Appendix 5.)
- VAS pain score
- VCSS (See Appendix 7.)
- Anticoagulation Review, based on the Extended Anticoagulation Protocol (See Appendix 2.)

9.9 12 Month Evaluation (365 days ± 60 days)

Patients that refuse the venogram and IVUS at this visit should have all other assessments listed here performed:

- Physical examination (to assess for the presence of Adverse Events)
- Assessment of primary patency by venography

STE-HUM-007P US Clinical Protocol Revision C

- Determination of residual external venous segment compression, stent recoil, and lesion coverage by IVUS
- Duplex ultrasound for all patients (For patients refusing the venographic assessment at this visit, DUS-determined patency will be used towards the primary efficacy endpoint instead.)
- Assessment of stent integrity by bi-plane X-Ray (See Appendix 3.)
- CIVIQ-2 Quality of Life questionnaire (See Appendix 5.)
- VAS pain score (See Appendix 6.)
- VCSS (See Appendix 7.)
- Anticoagulation Review, based on the Extended Anticoagulation Protocol (See Appendix 2.)

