9.10 Interval Evaluation

At any point following the venous stenting procedure, the patient may present with symptoms of clinically significant obstruction of the target vessel. Patients with possible obstruction should undergo all medical examinations and interventions as deemed appropriate for medical care. All technical examinations (DUS, IVUS, or venograms) obtained during the course of the evaluation will be submitted as part of the case report form and will be submitted to the Core Laboratory for determination of primary endpoint.

Patients who undergo re-intervention, but who are found on Core Laboratory assessment to have vessel patency prior to the re-intervention will not be counted as a primary efficacy endpoint failure. Patients who undergo an interval evaluation but do not receive an intervention will have their status (patency/non-patency) determined by the Core Laboratory. Patients who are found to be patent by Core Laboratory analysis will continue in the study through 12 months.

Patients who undergo another intervention at any time prior to the 12 month evaluation, or who are found to have in-stent stenosis > 50%, by Core Laboratory assessment, will be considered to have failed the primary efficacy endpoint and will not be required to have further assessment of vessel patency or other secondary endpoints.

All patients will complete the 30-day safety assessment regardless of primary patency status.

9.11 24 Month Evaluation (730 days ± 90 days)

- Telephone follow-up for SAE assessment. May be performed in-person, at the discretion of the investigator.
- Duplex ultrasound to assess vessel patency. (Office or laboratory visit)

9.12 36 Month Evaluation (1,095 days ± 90 days)

- Telephone follow-up for SAE assessment. May be performed in-person, at the discretion of the investigator.
- Duplex ultrasound to assess vessel patency. (Office or laboratory visit)

STE-HUM-007P US Clinical Protocol Revision C

Confidential

Page 31 of 70

9.13 48 Month Evaluation (1,460 days ± 90 days)

• Telephone follow-up for SAE assessment. May be performed in-person, at the discretion of the investigator.

9.14 60 Month Evaluation (1,825 days ± 90 days)

• Telephone follow-up for SAE assessment. May be performed in-person, at the discretion of the investigator.

STE-HUM-007P US Clinical Protocol Revision C

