15.8 Evaluation of Endpoints

15.8.1 Primary Efficacy Endpoint

The primary efficacy endpoint for this study will be the primary patency rate at 12 months post-intervention. Stented limbs will be assigned the status of *patency failure* if they are known to have a patency failure event:

- Thrombosis including the stented area of the vein
- Re-intervention including the stented area
- Venous imaging study at any time through 12 months showing a restenosis of greater than 50%.

Patients will be assigned the status of *patency success* if their venous imaging study at 12 months showed no greater than 50% restenosis (and no prior study showed greater than 50% restenosis).

STE-HUM-007P US Clinical Protocol Revision C

In the per-protocol (PP) analysis, only patients that meet either of these two criteria will be included. Patients with no imaging study at 12 months and no patency failure event will be ignored in the analysis.

In the worst-case and tipping point analyses, all patients will be included. Patients who were ignored in the PP analysis will be treated as patency failures.

Both the PP and worst-case analyses will test the following hypotheses:

$$\begin{aligned} \mathsf{H}_{0} &: q_{NT} * (p_{NT} - PG_{NT}) + q_{PT} * (p_{PT} - PG_{PT}) \le 0 \\ \mathsf{H}_{A} &: q_{NT} * (p_{NT} - PG_{NT}) + q_{PT} * (p_{PT} - PG_{PT}) > 0, \end{aligned}$$

where p_{NT} and p_{PT} are the observed 12-month patency rates for NT and PT subjects, respectively; PG_{NT} and PG_{PT} are pre-specified fixed performance goals for NT and PT subjects, respectively; and q_{NT} and q_{PT} , both are fixed weights for NT subjects (0.26) and PT subjects (0.74), respectively. The sample weights will not be adjusted based on actual enrollment rates.

The hypothesis test for this endpoint will be tested using a one-sided weighted Z-test at the 0.025 significance level. The test statistic for this hypothesis test is:

$$Z = \frac{q_{NT} * (p_{NT} - PG_{NT}) + q_{PT} * (p_{PT} - PG_{PT})}{\sqrt{q_{NT}^2 * \frac{PG_{NT}(1 - PG_{NT})}{n_{NT}} + q_{PT}^2 * \frac{PG_{PT}(1 - PG_{PT})}{n_{PT}}}$$

where p_{NT} is the proportion of successes in the NT population, PG_{NT} is the performance goal of 85.5% for the NT population, q_{NT} is the predefined weight of 0.266 for the NT population, p_{PT} is the proportion of successes in the PT population, PG_{PT} is the performance goal of 67.9% for the PT population, q_{PT} is the pre-defined weight of 0.74 for the PT population.

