16 CORE LAB ASSESSMENTS

16.1 Venogram Core Laboratory

A copy of all venographic studies collected in the study will be sent to the angiographic core laboratory for review. Venographic site assessment guidelines and shipping requirements will be provided by angiographic core lab (e.g., during the site training).

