16.2 Duplex Ultrasound Core Laboratory

All duplex ultrasound examinations collected through the 36 month follow-up of the study will be sent to the duplex ultrasound core laboratory for review and assessment. Duplex assessment guidelines, technician training (if required), and data submitting guidelines will be provided by the duplex ultrasound core laboratory (e.g., during the site training).

Pre-enrollment DUS is considered an investigator-determined inclusion criterion, and does not require Core Laboratory confirmation.

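### Section 15.8.1 does not say whether venogram or duplex decides 12-month patency when both exist and disagree, and no analysis compares the two

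*Combined protocol and SAP*

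**What the plan says.** **Endpoint.** Section 7.1 counts in-stent stenosis above 50% by venogram as loss of patency, then adds: "For patients refusing the venographic assessment at 12 months, DUS-determined patency will be used instead". Each test has its own baseline. Section 9.5.3 uses the post-stent venogram when a 12-month venogram exists. Section 9.6 covers refusers, "with the DUS obtained at the Discharge or Three Days Post-Procedure visit serving as the baseline".

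**Schedule.** Section 9.9 lists venography and also "Duplex ultrasound for all patients". Under 9.10, patients who have already failed "will not be required to have further assessment of vessel patency or other secondary endpoints".

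**Analysis rule.** Section 15.8.1 lists as a failure event: "Venous imaging study at any time through 12 months showing a restenosis of greater than 50" percent. Success requires a 12-month imaging study at or below that threshold and no earlier study above it. Neither rule names a modality or says which test prevails.

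**Reading.** Both tests are read centrally: "A copy of all venographic studies collected in the study will be sent to the angiographic core laboratory for review" (16.1), and "All duplex ultrasound examinations collected through the 36 month follow-up of the study will be sent to the duplex ultrasound core laboratory" (16.2).

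**Agreement.** Section 4.2 states: "There is no reported comparison between duplex ultrasound scanning and venography in the assessment of stent patency". It goes on to call venography the gold standard.

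**Sensitivity analyses.** Section 15.3.1 plans a worst-case and a tipping-point analysis, both for missing endpoints. A refuser with a DUS is not missing, so neither applies. No expected or maximum refusal rate is given.

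**The concern.** A patient who accepts venography will normally have two 12-month studies. If the venogram shows a patent stent and the DUS reads above 50%, section 7.1 gives a success. In 15.8.1 the same patient meets the failure bullet through the DUS and the success criterion through the venogram. The primary result would then depend on a choice made at analysis, possibly with the data in view.

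The second gap is that patients choose their own modality after treatment, and the plan has no check on what that does to the patency rate. DUS could err either way in refusers. Missed stenosis would raise the rate and the chance of a false success. False alarms would lower the rate and cost power.

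**Working it through.** **Inputs from the documents.** Assumed patency 0.779 (PT) and 0.955 (NT); goals 0.679 and 0.855; weights 0.74 and 0.26; 156 evaluable; one-sided 0.025 (15.7). Stenosis of 50% or more: 3% in PT (15.5.2 and Table 15.5.2.c) and 1% in NT (Table 15.5.2.a).

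**Assumptions.** 156 splits as 41 NT and 115 PT, following the weights. The documents give no refusal share *f* and no DUS accuracy, so both are varied. The venogram is taken as correct.

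**1. The plan's own figure.**
- Null SE = √(0.26²×0.855×0.145/41 + 0.74²×0.679×0.321/115) = 0.0352.
- SE at the design rates = √(0.26²×0.955×0.045/41 + 0.74²×0.779×0.221/115) = 0.0298.
- Power = Φ((0.10 − 1.96×0.0352)/0.0298) = 0.850.
- Summing the two binomial distributions exactly over the 15.8.1 rejection region gives 0.870. Neighbouring splits give 0.852 (39/117) and 0.832 (42/114).

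The stated 84% is reproduced within the discreteness of the test. The comparisons below use exact power with the 41/115 split, so their reference is 0.87.

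**2. DUS reads above 50% in a share *e* of patent stents.** Under the literal 15.8.1 rule every patent patient is exposed to the error, so the observed rate is p(1 − e). Under 7.1 only refusers are exposed, so it is p(1 − f·e).
- For e = 2%, literal rule: PT 0.779×0.98 = 0.763 and NT 0.955×0.98 = 0.936. The weighted loss is 0.02×(0.74×0.779 + 0.26×0.955) = 1.65 points.
- For e = 2%, 7.1 with f = 20%: PT 0.779×0.996 = 0.776 and NT 0.955×0.996 = 0.951. The loss is 0.33 points.

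| False-positive rate *e* | Power, literal 15.8.1 | Power, 7.1 with 20% refusal |
|---|---|---|
| 0 | 0.87 | 0.87 |
| 2% | 0.71 | 0.84 |
| 5% | 0.41 | 0.80 |

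**3. DUS misses every non-occlusive stenosis in refusers.** Inflation = f×(0.74×0.03 + 0.26×0.01) = f×0.0248. Type I error is computed exactly, with true patency at both goals.

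| Refusal *f* | Inflation (points) | One-sided type I error |
|---|---|---|
| 0 | 0 | 0.027 |
| 10% | 0.25 | 0.032 |
| 20% | 0.50 | 0.037 |
| 30% | 0.74 | 0.043 |
| 40% | 0.99 | 0.050 |

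Section 15.7 also requires both observed rates to exceed their goals. With that added, the same enumeration runs from 0.022 at no refusal to 0.040 at 40%.

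**4. What the paired data can show.** With 10–40% refusal, at most 140 to 94 patients have both tests. At 0.0248 per patient they hold about 3.5 to 2.3 non-occlusive stenoses. A sensitivity of 3 out of 4 has an exact 95% interval of 0.19 to 0.99. The table can reveal gross disagreement and estimate false positives reasonably well, but it cannot pin down sensitivity to stenosis.

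**The case against.** **The conflict may only be loose wording.** Section 7.1 uses DUS in place of venography only for refusers, and 9.5.3 and 9.6 assign baselines accordingly. The any-time clause in 15.8.1 fits the interval evaluations of 9.10. This is probably what was intended, so a reader should not infer that a second chance to fail is the established rule. But 15.8.1 is the operative analysis text and its clause covers the 12-month DUS. The section 1 definition of in-stent stenosis also admits venogram or DUS. The ambiguity stands.

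**DUS is a reasonable fallback.** The performance goals rest on patency by venogram or DUS (15.5.2), both tests go to core laboratories, and without the fallback refusers with no failure event would drop out of the analysis. All of that stands. It supports keeping DUS for refusers, but does not settle precedence or show agreement.

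**The type I error case is extreme.** It assumes that DUS misses every stenosis. Inclusion criterion 2 requires willingness to complete follow-up, so high refusal is not a given. Both points stand, and the figures in step 3 are upper bounds for missed stenosis at the documents' rates. Letting DUS miss 20–50% of all failures would give larger errors, but re-intervention is not read from DUS and 15.5.2 itself judges occlusion by DUS flow, so I do not rely on that case.

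**Conclusion.** The point holds as a defect of specification with a modest, two-sided effect. Sections 7.1 and 15.8.1 classify the same patient differently, and nothing planned would show how far the two tests agree. On the assumed 41/115 split, a 2% false-positive rate separates the two rules by about 0.13 in power (0.84 − 0.71). Missed stenosis in refusers adds at most about 1 point to patency and brings one-sided type I error to 0.032–0.050 for 10–40% refusal. The false-positive and refusal rates are assumptions, not figures from the plan.

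Three stronger conclusions are not supported:
- **That DUS flatters the device.** The documents give no DUS accuracy, so the direction is unknown.
- **That every patient will have a 12-month DUS.** Those who fail earlier are exempt under 9.10.
- **That the paired data could correct the primary result at no cost.** A correction would rest on perhaps two to four stenoses. It would assume that accuracy in acceptors carries over to refusers, and over the scenarios simulated it would leave power at roughly 0.85 to 0.71.

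**What to change.** 1. State in 15.8.1 that the core-laboratory venogram decides when both 12-month tests exist, that DUS is used only when venography is refused, and that earlier failures established at an interval evaluation (9.10) still count.
2. Prespecify a paired core-laboratory table of DUS against venogram with confidence intervals, and report the refusal rate.
3. Add, as supportive only, a tipping-point analysis over DUS sensitivity and specificity among refusers.
4. If a venogram-only analysis is run, say how failures before 12 months are handled. As an illustration, take 17.5% failing (0.74×0.221 + 0.26×0.045), half of them before 12 months, and 30% of the rest refusing. Keeping early failures while dropping refusers gives (8.75 + 6.125)/(8.75 + 63.875) = 20.5% failure. Dropping early failures too gives 6.125/63.875 = 9.6%. Either distortion exceeds the bias at issue.

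I would not re-run the primary test with results corrected for estimated sensitivity and specificity, for the reasons given in the verdict.

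The cost is SAP wording and a small amount of extra analysis of data already collected. No further imaging or patients are needed. The precedence sentence should be in place before the database is locked.
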